5.0 Amendments and Updates

- None.

6.0 Milestones

Major study milestones and their planned dates are as follows:

Start of Data Collection:	10-Mar-2017
End of Data Collection:	10-Dec-2017
Final Report of Study Results:	30-Mar-2018

7.0 Rationale and Background

Due to recent advances in antiviral drug development and rapid market entry, DAA-containing regimens have become the standard of care for HCV-infected patients in many countries [1]. Although the significant amount of studies have been already conducted and proven high efficacy and good safety of new regimens there is still a room for optimization of treatment schemes and duration of therapy in selected patient categories. Some easy-to-treat patients may require fewer components in the scheme and/or shorter treatment duration which allow improving tolerability, convenience and cost-efficacy of therapy.

Gt1b is the most prevalent genotype of HCV in Russia representing the majority of patients including those with liver cirrhosis [2]. According to Russian and international guidelines HCV-infected patients with liver cirrhosis require immediate treatment in order to prevent further deterioration of liver function and development of severe life-threatening complications like liver failure and hepatocellular carcinoma [1,3]. IFN-free regimens have significant advantages over IFN-containing regimens in this patient population with regard to efficacy, safety and convenience. As cirrhotic patients are being traditionally qualified as hard-to-treat, RBV is still widely used in this category even within IFN-free combinations. In the meantime despite general good safety profile of DAA combinations RBV can contribute to the development of anemia and other AEs

especially in patients with advanced fibrosis and cirrhosis [4]. Therefore exclusion of RBV from the regimens can improve treatment safety and further decrease the rate of discontinuation which will result in higher cure rate.

AbbVie 3D regimen contains 3 DAAs of different classes: paritaprevir – NS3/4A protease inhibitor boosted by ritonavir, ombitasvir - NS5A inhibitor and dasabuvir - non-nucleotide polymerase inhibitor. In phase III study TURQUOISE II 3D + RBV showed high efficacy and safety in GT1HCV-infected patients with compensated liver cirrhosis [5].

According to the recently published results of TURQUOISE III study Gt1b patients with cirrhosis can be successfully treated with 3D regimen without ribavirin [6]. In this study treatment-naïve and peginterferon/ribavirin treatment-experienced patients received 12 weeks of therapy with ombitasvir/paritaprevir/ritonavir (25/150/100 mg once daily) and dasabuvir (250 mg twice daily). Key inclusion criteria were hemoglobin ≥ 10 g/dL, albumin ≥ 2.8 g/dL, platelet count $\geq 25 \times 10^9/L$, creatinine clearance ≥ 30 ml/min, and Child-Pugh score ≤ 6 . Efficacy was assessed by the percentage of patients achieved sustained virologic response (HCV RNA < 25 IU/mL) 12 weeks post-treatment (SVR12). Efficacy and safety were assessed in all patients receiving study drug. Sixty patients with HCV GT1b infection and cirrhosis received treatment. The study population comprised 62% male, 55% treatment-experienced, 83% with IL28B non-CC genotype, 22% with platelet count $< 90 \times 10^9/L$, and 17% with albumin < 3.5 g/dL. All 60 patients completed treatment, and SVR12 was achieved in 100% (95% CI, 94.0 – 100%) of patients. The most common adverse events were fatigue (22%), diarrhea (20%), and headache (18%). Only one patient (1.7%) experienced a serious adverse event. Laboratory abnormalities were infrequently observed and not clinically significant. The HCV regimen of ombitasvir/paritaprevir/ritonavir and dasabuvir without ribavirin for 12 weeks achieved 100% SVR12 and was well tolerated in HCV GT1b-infected patients with cirrhosis, suggesting that this 12-week ribavirin-free regimen is sufficient in this population.

Current study was developed in order to assess RWE effectiveness and safety of 3D regimen without RBV in Gt1b patients with compensated cirrhosis in Russia.

8.0**Research Question and Objectives****8.1****Research Question**

- What is the effectiveness of the interferon-free 3DAA ABBVIE REGIMEN without RBV in patients with HCV Gt1b infection and compensated liver cirrhosis in a real life setting?

8.2**Objectives****8.2.1****Primary Objective**

- To describe the effectiveness of the interferon-free 3DAA ABBVIE REGIMEN without RBV in patients with HCV Gt1b infection and compensated liver cirrhosis as evidenced by sustained virological response at 12 weeks after the end of treatment in routine clinical practice.

8.2.2**Secondary Objectives**

- To describe the end-of-treatment (EoT) response rate
- To assess the rate of relapse (timeframe for assessing relapse - between EoT and SVR 12)
- To describe baseline characteristics of patients with HCV Gt1b and compensated cirrhosis treated with AbbVie 3D regimen.
- To collect information on co-morbidities and concomitant medications in cirrhotic patients in the Russian population
- To describe the tolerability of the ABBVIE REGIMEN

9.0 Research Methods

9.1 Study Design

This is a prospective, multi-center observational study in patients receiving the interferon-free ABBVIE REGIMEN without RBV. The prescription of a treatment regimen is at the discretion of the physician in accordance with local clinical practice and label, is made independently from this observational study and precedes the decision to offer a patient the opportunity to participate in this study.

Adult patients chronically infected with HCV and compensated liver cirrhosis, receiving the interferon-free ABBVIE REGIMEN will be offered to participate in this study during a routine clinical visit at the participating sites.

After written Authorization (Consent) for Use/Disclosure of Data form has been obtained, patient data including demographic data, HCV disease characteristics, co-morbidities, co-medication, treatment details, and laboratory assessments as recorded in the patient's medical records (source documentation) will be documented in the electronic case report form (eCRF). Patients will be observed for the duration of the ABBVIE REGIMEN therapy and for up to 12 weeks after treatment completion. No patient identifiable information will be captured, a unique patient number will be automatically allocated by the web based eCRF system once the investigator or designee creates a new patient file.

This study is focusing on collecting real-world data. Follow-up visits, treatment, procedures and diagnostic methods will follow physicians' routine clinical practice.

12-week routine treatment regimen will include at least two observational visits (Visit 1 and EoT) plus one 30 days safety follow-up visit and one 12 weeks follow-up visit (SVR12) after the last dose of ABBVIE REGIMENT. Additional observational visits between Visit 1 and EoT can be done in case of clinical necessity and physician decision.

9.2**Product Supply**

As this is a post-marketing observational study, AbbVie is NOT involved in the product supply since the drug is being used according to the approved market label and is to be prescribed by the physician under usual, current medical practice and is clearly separated from the decision to include the patient in the study.

9.3**Setting**

For the purpose of this program participants will be recruited and observed in approximately 5-7 national and regional hospitals/outpatient services.

9.4**Program Duration**

Enrollment will start in March 2017 and continue approximately 6 months and ABBVIE REGIMEN therapy will be administered according to physician's prescription and the local label to all enrolled subjects. All visits of the program will be organized according to routine clinical practice over 12 weeks of treatment period as well as 12 weeks follow-up period to assess the SVR12. All enrolled patients will be followed by a personal or telephone contact at 30 days after their last dose in the study.

9.5**Investigator selection criteria**

In order to assure credibility of the final results the below listed criteria will be considered during the recruitment process of physician/investigators:

- Physician licensed in infection diseases or gastroenterology;
- Physician is working at a national or regional hospitals or outpatient centers;
- Availability of patient population fulfilling the inclusion/exclusion criteria;
- Ability to appropriately conduct the observational program.

9.6**Inclusion Criteria**

ABBVIE REGIMEN will be prescribed by physicians according to the routine clinical practice. Patient can be included in the study if he/she will satisfy the following criteria:

1. Age \geq 18
2. Treatment-naïve or IFN/RBV-experienced adult male or female patients with confirmed CHC Gt1b and compensated liver cirrhosis, receiving therapy with the interferon-free ABBVIE 3D REGIMEN initiated not earlier than 2 weeks before the enrollment or the initiation is planned not later than 2 weeks after the day of enrollment in accordance to standard of care and in line with the current local label.
3. Patients must voluntarily sign and the Authorization (Consent) for Use/Disclosure of Data form prior to inclusion into the study.
4. Patient must not be participating or intending to participate in a concurrent interventional therapeutic trial.

9.7**Exclusion Criteria**

A patient will not be eligible for this PMOS if he/she fulfils the following criteria:

1. Co-administration RBV with the ABBVIE REGIMEN
2. Patients with Child Pugh B and C cirrhosis
3. Patients with a history of prior DAA therapy
4. Any other contraindications to the administration of ABBVIE REGIMEN according to the label

9.8**Description of Activities**

The patient visits will be scheduled based on routine clinical practice and prescription of consulting physician. Prescription of ABBVIE REGIMEN is clearly separated from the decision to include the patient in the study. However, it would be included at least two observational visits (Visit 1 and EoT) plus one 30 days safety follow-up visit and one 12 weeks follow-up visit (SVR12) after the last dose of ABBVIE REGIMEN. Additional observational visits between Visit 1 and EoT can be done in case of clinical necessity and physician decision.

Information for patients enrolled within 2 weeks after initiation of ABBVIE REGIMEN is collected at routine patient visits therefore baseline patient data should be taken from medical records.

In total, there will be at least four study visits. Please refer to Table 2 for observational documentation.

Table 2. Program Activities

Assessment/ Procedure (only available data to be collected; no diagnostic or monitoring procedures to be applied to the patients apart from those of routine clinical practice)	Visit 1	Treatment Period (on-treatment visits)	Post-treatment (PT) Period	
			Safety Follow-up Visit ^c	SVR 12 Follow-up Visit
Authorization (Consent) for Use/Disclosure of Data form	X ^a			
Inclusion/Exclusion Criteria	X			
Demographic information	X			
IL28B	X			
Relevant CHC disease characteristics	X			
Liver fibrosis stage	X			
CHC treatment history	X			
HCV genotype and subtype	X			
HCV RNA samples	X	X		X
Clinical chemistry and hematology	X	X		X
ABBVIE REGIMEN initiation documentation	X			
ABBVIE REGIMEN adherence		X		
Concomitant medication	X	X		X
Relevant medical history, co-morbidities	X			
SAE, non-serious AE and pregnancy reporting	X	X	X	X

Abbreviations: EoT = End of Treatment (at Week 12 or at premature discontinuation),

PT = Post-Treatment

a Written patient authorization or informed consent must be obtained before any data documentation in the eCRF

b Patients who prematurely discontinue should return to the site to document EoT data

c Tolerability documentation until PT week 4, visit can be done as telephone call contact

Collected data and planned activities within the observational program:

Visit 1

- Signing of the Authorization (Consent) for Use/Disclosure of Data form by patient
- Assignment of patient's identification number (two-digit center number + two-digit patient individual enrollment number)
- Inclusion/exclusion criteria verification
- Demographics (sex, age, race)
 - Interleukin 28B (IL28B) genotypes
- CHC disease characteristics
 - Year of diagnosis and probable mode of infection
 - Stage of liver fibrosis
- CHC treatment history
 - Naïve or experienced
- If experienced, most recent prior therapy and outcome Relevant medical history, co-morbidities and co-infections
 - Liver USG, CT scan
 - Last available AFP value
- Concomitant medication
- ABBVIE REGIMEN information

- Laboratory data

Key clinical chemistry

- ALT
(alanine-aminotransferase)
- AST
(aspartate-aminotransferase)
- γ -GT
(gamma-glutamyltransferase)
- Total bilirubin
- Albumin
- Creatinine
- AFP

Remarks

including upper limit of normal (ULN),
including ULN,
AST to platelet ratio index (APRI) and Fibrosis-4
Score/Index (FIB-4)* will be calculated
creatinine clearance[#] will be calculated

Key hematology

- Hb (Hemoglobin)
- Platelets
- Prothrombin time

or international normalized ratio (INR)

Virology

- HCV genotype and subtype
- HCV RNA

quantitative/ qualitative HCV RNA by polymerase chain
reaction (PCR) test

HIV-infected patients only

- CD 4 count
(cluster of differentiation 4)
- HIV RNA

most recent assessment

in copies/mL

*derived from patient's age, ALT, AST and platelets

[#]by Cockcroft-Gault-Formula based on creatinine, gender, age and weight

End of treatment visit and additional on-treatment visits

End of treatment visit and additional on treatment visits is scheduled by the physician per routine clinical practice. Likewise treatment, procedures and diagnostic methods will follow physicians' routine clinical practice.

The following will be documented:

- Laboratory data

Key clinical chemistry

- ALT
- AST
- γ -GT
- Total bilirubin
- Creatinine

Remarks

- including ULN
- including ULN,
APRI and FIB-4 will be calculated
- creatinine clearance will be calculated

Key hematology

- Hb
- Platelets

Virology

- HCV RNA

quantitative/ qualitative HCV RNA PCR test, see 9.8.1

HIV-infected patients only

- CD 4 count
- HIV RNA

most recent assessment
in copies/mL

- Concomitant medication
- Tolerability (non-serious AEs, SAEs) and pregnancies

Safety Follow-up Visit (personal or telephone contact)

- Tolerability (non-serious AEs, SAEs) and pregnancies

SVR 12 Follow-up Visit

Follow-up visit is scheduled by the physician per routine clinical practice. Likewise treatment, procedures and diagnostic methods will follow physicians' routine clinical practice.

The following will be documented:

- Laboratory data

Key clinical chemistry

- ALT including ULN
- AST including ULN, APRI and FIB-4, will be calculated
- γ -GT
- Total bilirubin
- Albumin
- Creatinine creatinine clearance will be calculated

Key hematology

- Hb
- Platelets
- Prothrombin time or INR

Virology

- HCV RNA quantitative/ qualitative HCV RNA PCR test, see 9.8.1

HIV-infected patients only

- CD 4 count most recent assessment
- HIV RNA in copies/mL

- Tolerability (non-serious AEs, SAEs)

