No data will be imputed for any effectiveness or safety analyses except for the analyses of the HCV RNA endpoints. When there is no HCV RNA value in a visit time window post-baseline, but prior to EoT, the closest values before and after the window, regardless of the value chosen for the subsequent and preceding window, will be used for the flanking imputation described below. If a patient has a missing HCV RNA value at a post-Visit 1

visit prior to EoT but has undetectable HCV RNA (with LLoD \leq 50 IU/mL) or unquantifiable, but detectable HCV RNA levels (with LLoQ \leq 50 IU/mL) at both the preceding and succeeding measurements, the HCV RNA level will be considered undetectable or unquantifiable, respectively, at this visit for this patient. In addition, if a patient has an unquantifiable HCV RNA level at the preceding measurement and an undetectable HCV RNA level at the succeeding measurement, or vice versa, the HCV RNA level will be imputed as unquantifiable at this visit for this patient. For virological response at EoT a corresponding backward imputation approach will be applied. This means if HCV RNA is missing at EoT, then unquantifiable or undetectable will be assumed for EoT, if the succeeding HCV RNA value is undetectable or unquantifiable. For SVR12 the single last available HCV RNA measurement \geq 84 days post-treatment will be used. Subsequent to this flanking and backward imputation, if the HCV RNA value remains missing at a specific time point, then the patients will be considered as virological failure at this time point (i.e. not undetectable or unquantifiable).

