9.13.4 Primary Effectiveness Endpoint

The percentage of patients achieving SVR12 (single last HCV RNA <50 IU/mL 12 weeks [i.e. at least 84 days] after the last actual dose of the ABBVIE REGIMEN) is the primary effectiveness endpoint.

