4.1 General study design and plan²

This is a post-marketing, prospective, multicenter, observational study in patients receiving the interferon-free ABBVIE REGIMEN (Paritaprevir/r – Ombitasvir \pm Dasabuvir) without RBV.

This study is focusing on collecting real-world data. Adult patients chronically infected with HCV and compensated liver cirrhosis, receiving the interferon-free ABBVIE REGIMEN will be offered to participate in this study during a routine clinical visit at the participating sites. The prescription of a treatment regimen is at the discretion of the physician in accordance with local clinical practice and label, is made independently from this observational study and precedes the decision to offer a patient the opportunity to participate in this study.

After written Authorization (Consent) for Use/Disclosure of Data form (hereinafter – written patient authorization form) has been obtained, patient data including demographic data, HCV disease characteristics, co-morbidities, co-medication, treatment details, and laboratory assessments as recorded in the patient's medical records (source documentation) will be documented in the eCRF. Information for patients enrolled within 2 weeks after initiation of ABBVIE REGIMEN is collected at routine patient visits therefore baseline patient data should be taken from medical records. No patient identifiable information will be captured, a unique

¹ The EoT time point is included in the analyzed interval.

² This section is based on the sections 9.1 "Study Design" and 9.8 "Description of Activities" of clinical study Protocol.

P16-253 (CITRIN) _ STATISTICAL ANALYSIS PLAN _ FINAL 2.0 _ 16 Mar 2018

patient number will be automatically allocated by the web based eCRF system once the investigator or designee creates a new patient file.

Follow-up visits, treatment, procedures and diagnostic methods will follow physicians' routine clinical practice.

In the study, patients will be observed for the duration of the ABBVIE REGIMEN therapy and for up to 12 weeks after treatment completion. 12-week routine treatment regimen will include at least two observational visits (Visit 1 and EoT) plus one 30 days safety follow-up visit and one 12 weeks follow-up visit (SVR12) after the last dose of ABBVIE REGIMEN. 30 days safety follow-up visit can be done as telephone call contact. Additional observational visits between Visit 1 and EoT can be done in case of clinical necessity and physician decision.

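### The stated observation period ends where the SVR12 sampling rule begins, and the two documents do not settle whether an HCV RNA sample taken shortly before day 84 counts

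*Protocol*

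**What the plan says.** **Text that sites work from.** Protocol 9.1 states: "Patients will be observed for the duration of the ABBVIE REGIMEN therapy and for up to 12 weeks after treatment completion". SAP 4.1 carries the same sentence. Protocol 9.4 plans "12 weeks of treatment period as well as 12 weeks follow-up period to assess the SVR12". On timing, Protocol 9.8 says: "The patient visits will be scheduled based on routine clinical practice and prescription of consulting physician". Sections 9.1 and 9.8 and Table 2 name an SVR12 follow-up visit at 12 weeks but give no earliest day and no range of days for it.

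**Text that the analysis works from.** Protocol 9.13.4 defines the primary endpoint as "single last HCV RNA <50 IU/mL 12 weeks [i.e. at least 84 days] after the last actual dose of the ABBVIE REGIMEN", and SAP 3.2 repeats this. Protocol 9.13.1 fills gaps only up to the end of treatment (EoT). Flanking imputation applies to visits before EoT, and then: "For virological response at EoT a corresponding backward imputation approach will be applied". For SVR12 it takes the last measurement at day 84 or later, and "if the HCV RNA value remains missing at a specific time point, then the patients will be considered as virological failure at this time point". Protocol 9.13.3 makes the core population (CP) the primary analysis set.

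**Text on windows.** Protocol 9.13.1 leaves the HCV RNA windows to the SAP. The only SVR12 window the SAP defines is in Table 4.2: the last value from day 57 to day 112 after the last dose, in a table introduced for clinical laboratory results. SAP section 6 then refers to an SVR12 time window for HCV RNA. SAP section 9 defines SVR12 at 12 weeks without mentioning 84 days.

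**The concern.** The SVR12 visit is the one that decides the primary outcome, and its timing is described differently to the people who book it and the people who analyse it. A centre that reads only the operational sections learns that follow-up lasts up to 12 weeks and that visits follow routine practice. Nothing there says that a sample a few days short of 12 weeks may be unusable.

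At stake is the primary SVR12 rate. A cured patient with a negative result just before day 84 and no later sample would be counted with the failures because of the appointment date, not the virology. Protocol 9.15 already warns that missing follow-up HCV RNA can make the SVR rate look too low; here the plan's own wording could add to that missingness. The rationale cites a trial with 60 responders out of 60, so even a few such cases could be read as weaker real-world effectiveness. Conversely, if the SAP window is used, the same patients count as successes, and the rate then rests on a reading of the window that neither document fixes.

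**Working it through.** **Inputs.** Observation up to 12 weeks (Protocol 9.1, SAP 4.1). Earliest accepted sample day 84 (Protocol 9.13.1 and 9.13.4, SAP 3.2). Missing SVR12 value counted as failure (Protocol 9.13.1). SAP window days 57–112 (Table 4.2). 60 patients (Protocol 9.11). Exact Clopper-Pearson 95% intervals (Protocol 9.13.6). Neither document gives the number of patients sampled early; call it k and vary it.

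**Step 1: the plan's own figures.** 12 × 7 = 84 days, so the endpoint's equation of 12 weeks with 84 days is right. For 60/60 the exact lower limit is 0.025^(1/60) = 0.940, which reproduces the 94.0–100% quoted in Protocol section 7.

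**Step 2: the two periods.** Observation up to day 84 and sampling from day 84 share, on a literal reading, one day. Of the 56 days in the SAP window (112 − 57 + 1), 27 (days 57–83) fail the 84-day rule and 29 (days 84–112) meet it.

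**Step 3: one patient through each rule.** Take a CP responder whose last HCV RNA, on day 80, is negative, with no later test for reasons unrelated to safety or effectiveness.

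| Rule | Result |
|---|---|
| Protocol 9.13.1/9.13.4, CP | No value at day 84 or later, nothing imputed: failure |
| SAP 3.2 with the SAP section 9 categories, CP | Missing SVR12 data, listed under non-response |
| Protocol CPSFU (CP with sufficient follow-up) | Excluded |
| SAP Table 4.2 window applied to HCV RNA | Inside days 57–112: success |

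Protocol 9.13.1 itself equates the SVR12 time window with day 84 or later. SAP section 6 borrows the term, but the SAP's only definition of it is days 57–112. Either reading can be defended from the text.

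**Step 4: size.** Assume all 60 patients are cured and in the CP, and k have their last sample on days 57–83. The Protocol rate is (60 − k)/60, so each case costs 1/60 = 1.67 percentage points. Limits are the 2.5% point of Beta(x, n − x + 1) and the 97.5% point of Beta(x + 1, n − x), with x = 60 − k and n = 60.

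| k | Protocol rule, CP | Days 57–112 applied |
|---|---|---|
| 0 | 100% (94.0–100) | 100% (94.0–100) |
| 1 | 98.3% (91.1–100.0) | 100% (94.0–100) |
| 3 | 95.0% (86.1–99.0) | 100% (94.0–100) |
| 6 | 90.0% (79.5–96.2) | 100% (94.0–100) |
| 12 | 80.0% (67.7–89.2) | 100% (94.0–100) |

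Under the Protocol's CPSFU rule, k = 6 gives 54/54 = 100% (93.4–100).

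**The case against.** The strongest reply is that the Protocol plainly expects data after day 84. Section 9.13.1 requires every HCV RNA measurement to be entered, the endpoint has no upper limit, and Table 1 in 9.13.7 labels the 12-week point day 85 and runs its laboratory window to day 112. This stands. A reader might infer that centres are barred from recording a later sample, or have no duty to, so that only day 84 itself can yield a valid result. The documents do not support that: the sentence in 9.1 is descriptive, and the entry rule carries no time limit. What remains is that the stated observation period does not extend over those later samples, and nothing asks a centre to look for one.

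A second reply is that a visit held at 12 weeks meets the rule, so an early visit would be a departure from the plan. That is fair, but no tolerance is stated in either direction and timing is left to routine practice.

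Third, the effect would be visible: the SAP lists missing SVR12 data separately, repeats its tables without those patients, and analyses the CPSFU. The SAP shells even label the CPSFU percentages as the main analysis. But Protocol 9.13.3 makes the CP primary, SAP section 15 declares no departure from the Protocol, and the extra tables do not repair the CP rate.

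Finally, a reader might centre a bell curve on day 84 and conclude that nearly half the visits would be early, or expect false differences between centres. The first is produced by the assumed curve, since the documents give no visit-day distribution. The second affects no planned analysis, because SAP 7.4 pools all centres.

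**Conclusion.** The point holds as an inconsistency that leaves the classification of some primary outcomes open. A responder last sampled shortly before day 84 is a failure under Protocol 9.13.1 and 9.13.4, and may be a success under the SAP's day 57–112 window. The gap is 1.67 percentage points per patient if 60 are analysed, and three such patients separate 100% from 95.0%. These figures assume that all 60 are cured and in the CP, and that no later sample exists for the patients concerned.

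The total effect cannot be estimated: it is zero if no one is sampled early, or if the SAP window governs HCV RNA. It would be wrong to say that the primary endpoint uniformly rejects early samples, or that a large downward bias has been shown. Because the study is descriptive and single-arm, and the supplementary tables would expose the effect, this is something that should be fixed rather than something that must be.

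**What to change.** 1. State one HCV RNA window for SVR12, identical in Protocol 9.1, 9.8 with Table 2, 9.13.1 and 9.13.4, and in SAP 3.2, 4.1 with Table 4.2, 6 and 9. One option is day 84 or later after the last actual dose, with an upper cut-off such as day 112. If a cut-off is adopted, say how a first sample after it is handled, since the endpoint now has no upper limit. If Table 4.2 is meant only for other laboratory data, say so.
2. Make the observation period in Protocol 9.1 and SAP 4.1 cover the whole window.
3. Label the SVR12 visit with that window in Protocol 9.8 and Table 2.
4. Add an eCRF check that flags an SVR12 HCV RNA date outside the window and asks for any later routine result.
5. Add a sensitivity analysis of SVR12 using days 57–112.

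The cost is a wording amendment, one edit check, up to about 4 more weeks of data entry per patient (112 − 84 = 28 days) and one extra table. No test outside routine practice is needed. The data-collection end date in Protocol section 6 (10 December 2017) should be aligned at the same time. With about 6 months of enrolment from 10 March 2017, a patient starting 12 weeks of treatment on 10 September 2017 reaches day 84 after the last dose only on 24 February 2018 (83 + 84 = 167 days later).
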